7.2 Serious Adverse Events

7.2.1 Definition

A serious adverse event (SAE) is any adverse event (experience) that in the opinion of either the investigator or sponsor results in **ANY** of the following:

- Death.
- A life-threatening adverse event (experience). Any AE that places a participant or participants, in the view of the Investigator or sponsor, at immediate risk of death from the reaction as it occurred. It does **NOT** include an AE that, had it occurred in a more severe form, might have caused death.
- Inpatient hospitalization or prolongation of existing hospitalization (for > 24 hours).
- A persistent or significant incapacity or substantial disruption of the ability to conduct normal life functions.
- A congenital anomaly or birth defect.
- Important Medical Event (IME) that, based upon medical judgment, may jeopardize the participant and may require medical or surgical intervention to prevent one of the outcomes listed above.

7.2.2 Reporting Serious Adverse Events

All new SAEs occurring from the date the participant signs the study consent until 90 days after the last intervention or a new treatment is started, whichever comes first, will be reported. The RPCI SAE Source Form is to be completed with all available information, including a brief narrative describing the SAE and any other relevant information.

SAEs occurring after the 90 day follow-up period that the investigator determines to be possibly, probably or definitely related to the study intervention should be reported.

SAEs that are unexpected and possibly, probably or definitely related must be reported as an Unanticipated Problem. Please refer to **Section 7.4** for details on reporting Unanticipated Problems.

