6.5 Criteria for Retreatment

- Patients with “severe” delayed gastric emptying assessed radiographically or clinically at any time will be considered for endoscopic procedures for gastric outlet obstruction, including pyloric botulinum toxin injection or balloon dilation, or operative procedure. This is irrespective of whether a patient was initially treated with botulinum toxin at the minimally invasive esophagectomy; patients randomized to the botulinum toxin group may undergo additional botulinum toxin injection endoscopically. The maximum dose of botulinum toxin a patient may receive for this study in the three-month period is 300 units. Each of these procedures- when a patient undergoes a therapeutic endoscopic procedure or returns to the operating room- will be defined as a secondary procedure.
- Development of “severe” delayed gastric emptying as assessed by nuclear medicine study will be considered a failure of the experimental procedure and will be included in the primary analysis. Requirement for secondary procedure or development of “severe” delayed gastric emptying as assessed by parameters other than the nuclear medicine study will be included in the secondary analysis.
- Patients with “moderate” delayed gastric emptying assessed radiographically or clinically at any time will be considered for initiation of promotility agents. Development of “moderate” delayed gastric emptying will be included in the secondary analysis.

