6.6 Outpatient Postoperative Follow-Up Visits

Study participants will be followed for data collection for 90 days (routine post-esophagectomy follow-up and surveillance, per standard of care). The following evaluations will be performed during the outpatient postoperative course, unless otherwise clinically indicated:

- In the postoperative period, patients return to office for outpatient follow-up approximately one to three weeks after discharge (“Postoperative Visit #1”). This visit is standard of care and can be scheduled per PI discretion. Physical exam and vital signs will be conducted at this visit. The dietician will assess oral intake, and supplemental tube feeds adjusted accordingly. Day until patient tolerates 75% and 100% of nutritional needs orally will be recorded as per nutritionist assessment.
- As a participant in this study, patients in both randomization groups will undergo a nuclear medicine emptying study. The nuclear medicine emptying study may occur within the window of Postoperative Visit #2 (\pm 14 days) to assess dynamic conduit function. This test can be extended beyond post-operative Visit #2 at PI’s discretion. Patients will be monitored for any symptoms of delayed gastric emptying during this time by questionnaire (See **Appendix C**), to determine if nuclear medicine study findings correlate with concurrent clinical symptoms.
 - Prior to the nuclear medicine emptying study, the patient must be fasting for at least 6 hours, including oral intake and any supplemental j-tube feeds. If the patient is a diabetic, the glucose level should be measured and less than 275 mg/dL within 2 hours of the study. Opiates must be held for 48 hours prior to the study. Patients should not be on any of the medications listed in **Appendix B** within the 48 hours prior to the study. Patients will remain in the nuclear medicine suite during this time, and will be required to sit upright, and may walk around the room. During the study, for the time between the images, the patients may be sitting, standing, or walking, but should remain in close proximity to the nuclear medicine facility.
- Post-surgical symptom evaluation based on clinical factors during the outpatient follow-up visits, and additionally by phone conversation between outpatient follow-up appointments if clinically indicated.

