7.1.2 Drug Information- Botulinum toxin

OnabotulinumtoxinA (botulinum toxin type A, Botox[©]) inhibits the release of acetylcholine from nerve endings at neuromuscular junctions in the local muscle (10). Without the release of acetylcholine, neurotransmission between peripheral nerve endings and muscle fibers cannot occur, and the muscle becomes weak or paralyzed (10). The inhibitory effect of botulinum toxin is temporary, and muscle function recovers at 3 months after administration. The effect is not immediate, and rather occurs within 1-3 days.

With intramuscular injection at a dose of 100 units, botulinum toxin is not expected to be in contact with the peripheral blood (10). In rare instances, botulinum toxin may spread from the area of injection and produce symptoms consistent with botulinum toxin effects (13). These unanticipated symptoms may include asthenia, diplopia, ptosis, dysphagia, dysphonia, urinary incontinence, and breathing difficulties. These symptoms have been reported hours to weeks after injection.

Incidence of side-effects depends on injection site location. For example, patients treated with botulinum toxin injection into the sternocleidomastoid muscle for cervical dystonia are more likely to have the side-effects of swallowing difficulties, due to local diffusion. Swallowing and breathing difficulties may be life-threatening, and there have been reports of death (11). Patients with history of underlying conditions predisposing to muscle weakness have an increased risk of these side effects occurring (11). However, due to the nature of this study, patients with underlying muscle weakness are excluded from this study.

The maximum recommended dose of OnabotulinumtoxinA, regardless of the indication, is 400 units over three months (10). Cervical dystonia is treated with doses ranging from 198-300 units, divided among the affected muscle, with maximum dose 50 units per site. Our proposed dosage, 100 units in divided doses into the pyloric muscle, is within the range used among other high-volume esophagectomy centers (2, 3, 8, 9).

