7.3 Follow-Up for Serious Adverse Events

All related SAEs should be followed to their resolution, until the study participant is lost to follow-up, the start of a new treatment, or until the study investigator assesses the event(s) as stable or irreversible. New information will be reported when it is received.

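### Section 7.2.2 stops reporting of new SAEs at an undefined new treatment, which leaves SAEs from then until day 90 outside required reporting

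*Combined protocol and SAP*

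**What the plan says.** Section 7.2.2 asks for all new SAEs from consent "until 90 days after the last intervention or a new treatment is started, whichever comes first". It then adds two rules. One covers "SAEs occurring after the 90 day follow-up period that the investigator determines to be possibly, probably or definitely related" to the study intervention. The other says that "SAEs that are unexpected and possibly, probably or definitely related must be reported as an Unanticipated Problem". Section 7.3 uses the same stop for events already reported: "All related SAEs should be followed to their resolution, until the study participant is lost to follow-up, the start of a new treatment" being one of the end points.

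The protocol defines neither the last intervention nor a new treatment.

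Three other sections bear on the window:

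- Section 6.6: "Study participants will be followed for data collection for 90 days". Section 4.2 and the synopsis say the same.
- Section 6.5 allows endoscopic botulinum toxin, balloon dilation or an operation for severe delayed emptying in either arm: "This is irrespective of whether a patient was initially treated with botulinum toxin at the minimally invasive esophagectomy". It labels each of these a secondary procedure and sets a study dose limit: "The maximum dose of botulinum toxin a patient may receive for this study in the three-month period is 300 units".
- Section 7.1.2, on symptoms of toxin spread: "These symptoms have been reported hours to weeks after injection".

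**The concern.** Two rules decide whether a new SAE is reported, and they do not meet. The main rule can end before day 90, when a new treatment starts. The late rule begins only after the 90-day period and covers related events only. Between the two is an interval, of a length set by the patient's course, in which the text requires no routine SAE report. This sits badly with collecting data on everyone for 90 days.

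The undefined terms make it worse. If an endoscopic re-injection or dilation is a new treatment, SAE reporting ends at the moment a patient is re-treated for delayed emptying, which is the outcome under study. The length of safety follow-up would then depend on that outcome, and the arm with more re-treatment would have less of it. If omitting botulinum toxin is to be recommended on the strength of this trial (section 1.2, Benefits), serious harm should be ascertained over the same period in both arms.

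**Working it through.** The plan gives no figure for SAE ascertainment, so there is nothing to reproduce. The check has two parts.

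**1. Does another route cover the interval from a new treatment to day 90?**

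- *Late related SAEs (7.2.2).* No. This rule starts only after the 90-day period.
- *Unanticipated Problems (7.2.2, 7.4).* In part. No stop at a new treatment is stated, but the event must be both unexpected and related. Section 1.2 lists aspiration, pneumonia and a longer hospital stay as risks of omitting the injection, so these would usually count as expected.
- *Routine AEs (7.1.4).* No. The window is 30 days after the last intervention, and the start of a new treatment is again listed as an end point.
- *Deaths (6.6).* In part. Date and cause are required for deaths within 30 days of surgery. A death on days 31 to 90 that follows a new treatment is covered by neither this rule nor routine SAE reporting.
- *Clinical events of interest and the day-90 call (6.7, 7.1, Table 2).* Pneumonia, aspiration, respiratory failure, further procedures and adverse events are asked about up to day 90, with no stop at a new treatment. This recovers many of the facts, but it is not SAE reporting. Section 11.1 puts study data in REDCap and sends adverse event data to a separate system for the monitoring committee.

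The gap in formal SAE reporting is therefore real, and it mainly affects SAEs that are unrelated or expected.

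**2. How large is it if every secondary procedure counts as a new treatment?**

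Inputs: 25 patients per arm (50 randomized 1:1, section 9.1); rates of additional procedures of 3.9% with and 15.9% without botulinum toxin (section 9.4, from one previous study). The re-treatment day d is not given and is assumed to lie between 14 and 56.

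Patients cut off = 25 × rate:

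- Botox: 25 × 0.039 = 0.975, about 1.
- No Botox: 25 × 0.159 = 3.975, about 4.

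Share of the arm's 90-day SAE follow-up lost = rate × (90 − d)/90:

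| Assumed day d | (90 − d)/90 | Botox | No Botox |
|---|---|---|---|
| 14 | 76/90 | 3.3% | 13.4% |
| 28 | 62/90 | 2.7% | 11.0% |
| 42 | 48/90 | 2.1% | 8.5% |
| 56 | 34/90 | 1.5% | 6.0% |

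Direction, comparing two independent Binomial(25, rate) counts of patients cut off:

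| Rates, Botox v no Botox | More in no Botox | Tie | More in Botox |
|---|---|---|---|
| 3.9% v 15.9% (plan) | 0.89 | 0.07 | 0.04 |
| 10% v 10% (assumed) | 0.40 | 0.19 | 0.40 |
| 15.9% v 3.9% (reversed, assumed) | 0.04 | 0.07 | 0.89 |

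On the other reading, a re-injection is a further intervention and restarts the 90 days. A re-injection on day 14 would then carry reporting to day 14 + 90 = 104, and one on day 56 to day 146, instead of ending it on day 14 or day 56. The same patient's window differs by 90 days according to an undefined word.

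Postoperative cancer therapy could also be a new treatment, but the protocol describes only neoadjuvant therapy. If 10% to 50% of patients started it between day 42 and day 70 (assumptions), the loss would run from 0.10 × 20/90 = 2% to 0.50 × 48/90 = 27% of follow-up. The documents give no reason for this to differ by arm.

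**The case against.** The strongest reply is that re-treatment is probably not a new treatment at all. Section 6.5 is about retreatment, calls each such procedure a secondary procedure, and counts repeat toxin within a dose limit for this study. Repeat toxin fits the last intervention at least as well, and would then lengthen the window. This stands: loss of SAE reporting after re-treatment is one reading only, and the figures above are conditional on it.

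Second, a reader might infer that serious events in this interval are lost to the trial. The documents do not support that. Section 9.4 compares pulmonary complications and additional procedures within three months between arms, with no stop at a new treatment, and the day-90 call asks about the same events. Unexpected related SAEs keep their own route.

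Third, a reader might infer that the under-count probably falls on the no-Botox arm and makes omission look safer. That follows from the 15.9% v 3.9% pair, but not from the plan's own hypothesis of no benefit, nor from the cited study that found more delayed emptying after botulinum toxin (both in section 1.2). Section 9.4.1 plans only frequencies by grade, without a between-arm test. Follow-up time lost is also not the same as SAEs lost, since the documents say nothing about when SAEs occur.

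None of this closes the gap. Under any reading in which some treatment is new, SAEs from its start to day 90 fall outside routine reporting, and the remaining routes are narrower or are not SAE reporting.

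**Conclusion.** The point holds as a defect in the SAE reporting rule. On the literal text, SAEs between a new treatment and day 90 are outside required SAE reporting unless they qualify as Unanticipated Problems, and this conflicts with 90-day data collection for every patient. The passages must be reconciled.

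The size depends on what a new treatment is. If it includes every secondary procedure, if the cited procedure rates apply, and if re-treatment falls between day 14 and day 56, about 4 v 1 of 25 patients are cut off (no Botox v Botox). The corresponding loss is about 13% to 6% v 3% to 1.5% of 90-day SAE follow-up. Whatever the direction, the arm with more re-treatment would have the shorter SAE follow-up on that reading. If re-injection is an intervention, it cuts off nothing.

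The primary analysis, sample size, power and alpha are untouched. What is at stake is complete and equal reporting of serious events to the monitoring committee and in the final safety tables.

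**What to change.** 1. In section 7.2.2, delete the clause that ends reporting at a new treatment. Suggested wording: *All SAEs will be reported for every participant from consent until the later of day 90 after esophagectomy and 90 days after the last study intervention, whether or not another treatment is started.* Taking the later date matters: a window fixed at day 90 after surgery would shorten reporting after a late re-injection if that counts as an intervention.
2. State whether repeat botulinum toxin and the other secondary procedures count as an intervention for this purpose.
3. Record the date and type of any new treatment, so that SAEs can be tabulated before and after it.
4. Remove the matching new-treatment stop in section 7.3.
5. Keep the existing rule for related SAEs after the window closes.

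The cost is protocol wording and some additional SAE forms. Some SAEs caused by other therapy will be reported; attribution and dates allow them to be separated. With the change, no patient's SAE follow-up to day 90 is cut off by this rule in either arm.

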7.3 Follow-Up for Serious Adverse Events

All related SAEs should be followed to their resolution, until the study participant is lost to follow-up, the start of a new treatment, or until the study investigator assesses the event(s) as stable or irreversible. New information will be reported when it is received.

7.4 Unanticipated Problems

7.4.1 Definition

An Unanticipated Problem (UP) is any incident, experience, or outcome that meets all of the following criteria:

- Unexpected (in terms of nature, severity, or frequency) given:
 - a) The research procedures that are described in the study-related documents, including study deviations, as well as issues related to compromise of participant privacy or confidentiality of data.
 - b) The characteristics of the participant population being studied.
- Related or possibly related to participation in the research (possibly related means there is a reasonable possibility that the incident, experience, or outcome may have been caused by the procedures involved in the research).
- Suggests that the research places participants or others at a greater risk of harm (including physical, psychological, economic, or social harm) than was previously known or recognized or if in relation to an AE is deemed **Serious** per **Section 7.2**.

7.4.2 Reporting Unanticipated Problems

The Reportable New Information (RNI) Form will be submitted to the CRS Quality Assurance (QA) Office within 1 business day of becoming aware of the Unanticipated Problem. After review, the CRS QA Office will submit the RNI to the IRB.

When becoming aware of new information about an Unanticipated Problem, submit the updated information to the QA Office with an updated Reportable New Information Form. The site

Investigator or designated research personnel will report all unanticipated problems to the IRB in accordance with their local institutional guidelines.

8 DATA AND SAFETY MONITORING

The Roswell Park Data Safety Monitoring Committee will assess the progress of the study, the safety data, and critical efficacy endpoints (Phase I studies will be reviewed quarterly; Phase II, III and pilot investigator-initiated studies will be reviewed semi-annually). The DSMC will review the study and will make recommendations that include but not limited to; (a) continuation of the study, (b) modifications to the design (c) suspension of or (d) termination of the study

9 STATISTICAL METHODOLOGY

The primary objectives of this study are:

- Determine if intra-pyloric botulinum toxin injection during a minimally invasive esophagectomy decreases postoperative occurrence of delayed gastric emptying, as assessed radiographically by nuclear medicine emptying study.

The secondary objectives of this study are:

- Determine if intra-pyloric botulinum toxin injection during a minimally invasive esophagectomy reduces the number of repeat procedures for delayed gastric emptying within 90 days, decreases time to oral intake meeting 100% of nutritional requirements, reduces the incidence of pulmonary and gastrointestinal complications directly related to delayed gastric emptying, reduces hospital length of stay related to delayed gastric emptying, and increases patient quality of life.

9.1 Sample Size Determination

The sample size justification is based on the primary analysis. We consider a study design with a total sample of $n=50$ patients (randomly assigned in a 1:1 fashion to the Botox and non-Botox treatment arms) and an interim analysis at $n_1=30$. The performance of this study design and decision rules (described in the primary analysis) was assessed via simulation study.

If the true rates of delayed gastric emptying are 0.30 and 0.70 in the Botox and non-Botox treatment arms, then the study design achieves 85.0% power to detect a significant change in the delayed gastric emptying rates at a significance level of 0.05. The chance of stopping early for superiority is 42.8%, while the chance of stopping early due to inferiority is only 1.0%.

If the true rate of delayed gastric emptying is 0.70 in both treatment arms, then there is a 4.3% chance of falsely identifying the Botox arm as superior (observed type I error rate), a 0.9% chance of stopping early for superiority, and a 42.1% chance of stopping early for inferiority.

9.2 Randomization

Patients will be randomized in a 1:1 fashion to the Botox and non-Botox treatment arms using a permuted block design. Participants will be stratified on the receipt of neoadjuvant chemoradiotherapy, smoking status, and diabetes. Participants will be randomized prior to the

minimally invasive esophagectomy, after signing consent for the surgical procedure. The randomization list will be developed by the Department of Biostatistics and Bioinformatics and provided to the study coordinator, who will then relay the information to the surgical team at the start of the procedure.

9.3 Demographics and Baseline Characteristics

Descriptive statistics (as appropriate: n, percent, mean, median, min and max) will be used to summarize demographic and baseline characteristics.

9.4 Primary and Secondary Analyses

Primary Analysis: A recent study demonstrated that patients who received Botox had a delayed gastric emptying rate of approximately 30% as compared to a complication rate in historical controls of 70% in patients that did not receive botulinum toxin injection (7). A retrospective review of patients undergoing minimally invasive esophagectomy at Roswell Park Cancer Institute indicates that the rate of postoperative delayed gastric emptying is even lower, however, this rate is based on very stringent criteria for delayed gastric emptying- requirement of a secondary procedure. Therefore, the primary objective is to determine if intra-pyloric botulinum toxin injection during a minimally invasive esophagectomy decreases postoperative occurrence of delayed gastric emptying. The primary outcome is delayed gastric emptying (assessed radiographically by nuclear medicine emptying study) which is treated as a dichotomous variable.

Patients will be stratified by receipt of neoadjuvant chemoradiotherapy, smoking status, and diabetes; and randomized in a 1:1 to the botulinum and non-botulinum treatment arms. The primary objective will be assessed using the intent-to-treat principle and a one-sided Cochran-Mantel-Haenszel (CMH) s test about the following hypotheses:

$$\begin{aligned} H_0: \theta &\geq 1, \\ H_A: \theta &< 1 \end{aligned}$$

where θ is the common odds ratio (COR) for the odds of delayed gastric emptying rates for the botulinum versus non-botulinum treatment arms. A one-sided test is performed as the rate of delayed gastric emptying is expected to decrease in the botulinum arm over the non-botulinum arm; that is, we expect $\theta < 1$.

The analysis will proceed in two stages using an O'Brien-Fleming alpha spending function. An interim analysis will be conducted after $n_1=30$ patients have completed treatment and the final analysis will be conducted after $n=50$ patients have completed treatment. The following decision rules will be utilized at each analysis:

Analysis	Decision Rule
Interim	
• If $p\text{-value} \leq 0.011396$, then reject H_0 and stop due to superiority.• If $\hat{\theta} > 1$, then stop due to inferiority.• Otherwise enroll $n_2=20$ patients.
Final	
• Reject H_0 if $p\text{-value} \leq 0.046533$

Secondary Analysis: The secondary outcomes include additional postop procedures, clinically assessed delayed gastric emptying (days to resumption of oral feeding, EORTC QLQ-30 QoL scores, and clinical symptoms of regurgitation, vomiting, and aspiration), delayed gastric emptying assessed by the gastrografin swallow exam/CT esophagram, pulmonary complications (aspiration, respiratory failure requiring reintubation, pneumonia within 3 months of surgery), and hospital length of stay. All variables will be reported by treatment arm using the appropriate descriptive statistics and graphical summaries.

The days to resumption of oral feeding, QoL scores and, hospital length of stay will be compared between treatment arms using the two sided independent-sample, stratified T-test. Normality will be assessed using the Anderson-Darling test and transformations (such as Box-Cox) will be applied, as appropriate. Bootstrap or non-parametric methods will be applied if no normalizing transformations can easily be applied. The rates of moderate clinical delayed gastric emptying (clinical signs of regurgitation, vomiting, and aspiration), moderate delayed gastric emptying (score of 2 or 3 on the gastrografin swallow test/CT esophagram), severe delayed gastric emptying (score of 4 or 5 on the gastrografin swallow test/CT esophagram), and pulmonary complications will be compared between treatment arms using the two-sided CMH exact test.

A previous study demonstrated that the rate of additional postoperative procedures may be lower for patients treated with botulinum (3.9%) as compared to those without botulinum (15.9%). Therefore, the rates of additional postop procedures within 3 months of the original procedure will be compared between treatment arms using a one-sided CMH exact test.

All analyses will be performed in SAS v9 (Cary, NC).

